The aim of the clinical trial is to evaluate the performance and safety of the ready-to-use filling material PA1704 compared to BioRoot™ RCS.

Main objective:

Evaluation of the 2-year efficacy rate of endodontic treatment determined on the basis of radiological and clinical criteria.

The radiological criteria will be assessed by independent blind reviewers; the clinical criteria will be assessed by the investigator.

Secondary objectives:

- Evaluation of the 6-month efficacy rate determined on the basis of radiological and clinical criteria,
- Evaluation of the 12-month efficacy rate determined on the basis of radiological and clinical criteria,
- Evaluation of the efficacy of the PA1704 ready-to-use filling material at 3.5 years and 5 years, determined on the basis of radiological and clinical criteria,
- Radiological assessment of the quality of the apical filling:
 - Adequate obturation length versus over-obturation and under-obturation (evaluated at T0 using an immediate post-op X-ray scan),
 - Density (radiopacity + vacuity) assessed at T0, 6 months, 12 months, and 24 months for the 2 filling materials, and additionally assessed at 3.5 years and 5 years for the PA1704 ready-to-use filling material,
 - Resorption of extruded material in the periapical space in the event of over-filling; assessed at 6 months, 12 months and 24 months for the 2 filling materials, and further assessed at 3.5 years and 5 years for the PA1704 ready-to-use filling material,
- Description of the pain experienced by the patient in the 7 days post-operation.
- Description of the use painkillers taken orally during the 7 days post-operation (frequency, cumulative dose, class of painkiller),
- Assessment of tooth functionality and pain on percussion at each follow-up visit (coronal restoration at 45 days, 6 months, 12 months and 24 months for the 2 filling materials, and additionally assessed at 3.5 years and 5 years for the PA1704 ready-to-use filling material).
- Evaluation of adverse events occurring after endodontic treatment (continuous evaluation up to 24 months for the BioRoot™ RCS filling material, and up to 5 years for the PA1704 ready-to-use filling material),
- Description of the surgical technique for first-line endodontic treatment (ET) or repeat endodontic treatment (RET) and any perioperative complications,
- Evaluation of operator comfort and satisfaction with the use of the filling material.

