If the patient is seen for treatment outside the protocol (routine care) or for any emergency, the investigator shall collect all the information relevant to the trial (date of consultation, reason for consultation, occurrence of AEs, etc.).

V3 — Clinical follow-up visit at 6 months (± 1 month) — Standard practice

- **Clinical examination**: Verification of the functional status of the treated tooth and percussion test (lateral and axial),
- Recording of AEs.
- Retro-alveolar X-ray check to evaluate the results of endodontic treatment at 6 months: 1) density of the root canal filling (radiopacity + presence of voids), 2) progress of resorption of the extruded material

where appropriate, **3)** apical lesion (absence/appearance/still present compared with T0) and progress of the size of an existing lesion (reduction, stabilization or increase).

Upload the 6-month follow-up retro-alveolar image to the eCRF (reminder: the entire tooth – from the *crown to the apex, including the root* – must be visible in the image; see chapter 6.1).

— The investigator shall evaluate the efficacy of the endodontic treatment on the basis of the clinical and radiological criteria identified (*Note: Only the evaluation of the radiological criteria by the independent reviewers will be taken into account for the primary evaluation criterion (PEC); the investigator's evaluation is to be used to determine further clinical follow-up*).

Procedure in the event of the appearance of a lesion or an increase in the size of a pre-existing lesion:

- If the investigator considers it to be an emergency (e.g. if the tooth is symptomatic and/or non-functional): the investigator will notify the patient of the failure of the endodontic treatment and schedule retreatment. In this case, the patient leaves the trial early due to the failure of the treatment and continues endodontic treatment outside the trial (end-of-trial form to be completed in the eCRF). Performance and safety evaluations now end. Failure notified at 6 months is carried forward as the PEC value (response at 24 months = failure). The patient will not be replaced.
- If the investigator considers that it is NOT an emergency (e.g. if the tooth is asymptomatic): medical advice should be sought from the trial coordinator (who will review the X-rays) before considering retreatment and early discharge from the trial for treatment failure.

V4 — Clinical follow-up visit at 12 months (± 1 month) — Standard practice

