- **Clinical examination**: verification of the functional status of the treated tooth and percussion test (lateral and axial),
- Recording of AEs.
- **Retro-alveolar X-ray check** to evaluate the results of endodontic treatment at 12 months: 1) density of the root canal filling (radiopacity + presence of voids), 2) progress of resorption of the extruded material where appropriate, 3) apical lesion (absence/appearance/still present compared with T0) and progress of the size of an existing lesion (reduction, stabilization or increase).

Upload the 12-month follow-up retro-alveolar image to the eCRF (reminder: the entire tooth – from the *crown to the apex, including the root* – must be visible in the image; see Chapter 6.1).

— The investigator will evaluate the efficacy of the endodontic treatment on the basis of the clinical and radiological criteria identified (*Note: Only the evaluation of the radiological criteria by the independent reviewers will be taken into account for the primary evaluation criterion (PEC); the investigator's evaluation will be used to determine further clinical follow-up*).

Procedure in the event of the appearance of a lesion or an increase in the size of a pre-existing lesion:

- If the investigator considers it to be an emergency (e.g. if the tooth is symptomatic and/or non-functional): the investigator will notify the patient of the failure of the endodontic treatment and schedule retreatment. In this case, the patient leaves the trial early due to the failure of the treatment and continues endodontic treatment outside the trial (end-of-trial form to be completed in the eCRF). Performance and safety evaluations now end. Failure notified at 12 months is carried forward as the PEC value (response at 24 months = failure). The patient will not be replaced.
- If the investigator considers that it is NOT an emergency (e.g. if the tooth is asymptomatic): medical advice should be sought from the trial coordinator (who will review the X-rays) before considering retreatment and early discharge from the trial for treatment failure.

V5 — Clinical follow-up visit at 24 months (± 1 month) — Standard practice

- **Clinical examination**: verification of the functional status of the treated tooth and percussion test (lateral and axial),
- Recording of AEs.

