14.2.1. Recording an adverse event

All AEs, whether or not related to the medical device under investigation or comparator, or to the endodontic treatment procedures, reported by the patient or observed by the investigator must be reported in the eCRF, specifying 1) the nature (clinical signs, symptoms, diagnoses), 2) the date and time of onset, 3) the duration, 4) end date and time, 5) the severity, 6) the therapeutic consequences, the ensuing evolution, and 7) relationship with the DM under investigation or the comparator DM or the endodontic treatment procedures (according to the investigator's opinion).

Clinical signs, symptoms and diagnoses should be described by the investigator/reporter using precise terminology, avoiding ambiguity and abbreviations; the location of symptoms may be specified if relevant. Based on this information, the CRO will code each AE using the IMDRF dictionary – appendices E and F (IMDRF, 2020).

Further instructions on how to register an AE can be found in the eCRF user guide provided by the CRO.

Health conditions related to the dental pathology studied which change during the clinical trial, and which are attributable to a lack of effectiveness of the medical device (e.g. failure of the endodontic treatment), are NOT considered as AEs and should therefore not be recorded as such.

Previous or ongoing medical conditions known at study entry should NOT be considered as AEs unless worsening has occurred. In this case, if a deterioration or exacerbation of an intercurrent condition previously reported in the patient's medical history occurs, the AE must be described using appropriate terminology (e.g. deterioration, exacerbation, etc.).

In the case of surgery or diagnosis, the cause leading to such a procedure is considered to be the AE rather than the procedure itself. In the case of death, the cause of death is considered to be the AE and the death its consequence.

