14.2.4. Type and duration of follow-up of subjects after an AE

AEs will be followed by the Investigator until they are resolved (i.e. the event is resolved or the pathology is unlikely to change or the subject is lost to follow-up). All clinical and biological examinations deemed necessary by the investigator will continue until the patient returns to normal. The investigator will provide the sponsor with copies of all examination results and treatments related to the follow-up of events.

14.2.5. Reporting of serious adverse events (SAEs) to the sponsor:

As part of this category 1 research involving human beings, the investigator is obliged to notify the sponsor immediately, and for no more than 3 calendar days, of any serious adverse event occurring during the study in an included patient (MDCG 2020-10/1). The people who should be contacted are listed in the 14.5 section.

1/ Initial declaration:

This initial report should be made on a paper form entitled "Initial report of a serious adverse event" (blank form kept in the Trial Master File of the investigating site), indicating the date of occurrence, the severity, the relationship with the device under investigation or comparator (or the protocol) and the follow-up. The narrative report must be completed and sent to the CRO and the sponsor as soon as any new relevant information is obtained. Depending on the nature and seriousness of the event, anonymized copies of the patient's source documents may be attached. The information to be collected on the paper form for the initial notification of an SAE is as follows:

- Clear identification of the Investigator/Rapporteur with all contact details,
- Detailed identification of the subject (patient identifier in the study, site number, patient age at the start of the SAE, sex),
- Subject treatment group (device under investigation or comparator),
- Date of endodontic treatment (start date of treatment and date of root canal filling if different from start date),
- Description of the event (free text): nature of the symptoms observed, duration and severity of
 the symptoms, date of onset of the first signs of the AE (before it becomes an SAE), patient
 history and current treatments,
- The reason why this event is considered serious,
- The Investigator's opinion on the imputability of the medical device under investigation or the comparator or the investigation protocol (unrelated, possible, probable, certain),
- Corrective action and treatment.

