The status of the SAE must be classified as follows:

- Resolved,
- Resolved with sequelae,
- In progress,
- Death.

The date on which the AE was resolved must be added; if the AE is still in progress, "Not Applicable" should be entered.

Following submission of the initial paper report form, the Investigator/Rapporteur must respond to any follow-up requests or queries from the Sponsor in relation to the SAE within the same timeframe as for the initial report. All the above contacts will be systematically copied on any exchanges concerning an SAE.

The Investigator must also report all SAEs in the eCRF by completing an AE form page.

If the SAE results in the patient being withdrawn early from the study, the Investigator must give details of the reason in the comments section of the initial paper declaration form.

2/ Follow-up declaration:

The Investigator must draw up a specific clinical report and complete and send the "follow-up SAE form" to the CRO and the sponsor within the same timeframe as mentioned above. Test results and hospital reports should be sent to the e-mail addresses listed in the 14.5 section. SAEs must be monitored until they are resolved or stabilized.

3/ After completion of the study:

All SAEs, whatever their relationship with the medical device or the protocol, occurring within 30 days of the last visit of each patient must be notified to the Sponsor in the same way as mentioned above. Any event occurring at any time after the end of the study for a subject who participated in the study and which could be related to the medical device under investigation in the opinion of the Investigator should also be reported to the CRO and the Sponsor.

14.2.6. Urgent safety problem

Any serious threat to public health (as defined in section 14.1) must be reported immediately to the sponsor (contact persons: See section 14.5).

14.2.7. Pregnancy

Pregnancies occurring after the date of signature of the informed consent and up to study discharge (whether early or not) will not be considered a serious adverse event insofar as no genotoxic effect of the medical device under investigation or comparator has been demonstrated; they will be recorded by convention in the AE pages of the eCRF.

14.2.8. Responsibility of the sponsor:

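### The emergency branch of section 6.5.2 ends safety evaluation when a failing patient leaves for retreatment, while sections 14.2.4 and 14.2.5 require safety follow-up to continue; the passages need reconciling

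*Combined protocol and SAP*

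**What the plan says.** Section 6.5.2 sets out what happens at V3 (6 months), V4 (12 months) and V6 (3.5 years, PA1704 arm) if a lesion appears or grows. When the investigator considers the case an emergency, the failure is notified, retreatment is planned, and "the patient leaves the trial early due to the failure of the treatment and continues endodontic treatment outside the trial". The end-of-trial form is completed and "Performance and safety evaluations now end". At V3 and V4 the failure also becomes the 24-month primary outcome: "Performance and safety evaluations now end. Failure notified at 6 months is carried forward as the PEC value", with the same wording at 12 months.

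The general provisions at the start of section 14 tie tolerance monitoring to the patient's participation, so they too stop it at exit.

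Other parts of section 14 point the other way:

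- Section 14.2.4: "AEs will be followed by the Investigator until they are resolved". The rule also stops if the condition is unlikely to change or the patient is lost to follow-up. Leaving for treatment failure is not among these stopping points.
- Section 14.2.5: SAEs are monitored until they resolve or stabilise, and SAEs of any causality "occurring within 30 days of the last visit of each patient must be notified to the Sponsor". The sentence after that keeps any later event reportable, without time limit, if the investigator thinks it could be related to the investigational device.

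Section 5.1 lists as an objective: "Evaluation of adverse events occurring after endodontic treatment (continuous evaluation up to 24 months" for BioRoot RCS, and to 5 years for PA1704. Section 14.2.1 excludes from AE recording conditions "attributable to a lack of effectiveness of the medical device (e.g. failure of the endodontic treatment").

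**The concern.** The two sets of instructions meet at one moment: the patient has a lesion, typically with a symptomatic or non-functional tooth, and the sealer is about to be disturbed or removed. The visit procedure is the page a site is likely to have open. Read literally, it releases the site from safety work that section 14 still requires.

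This matters more than an ordinary wording clash for three reasons. The protocol describes this as the first use of PA1704 in humans and says its adverse effects are not known. No data monitoring committee is planned. And section 7.7.6 compares the proportions of AEs and of patients with AEs between arms without mentioning how long each patient was observed, so safety collection that stops at failure makes observation time depend on efficacy.

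**Working it through.** The conflict itself is textual. Arithmetic is needed only for scale.

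**1. The passages side by side, for a patient leaving through the emergency branch**

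| Type of event | 6.5.2 (emergency branch) | Section 14 |
|---|---|---|
| AE present at the failure visit | Recorded at that visit before exit | Recorded |
| AE still open at exit | Safety evaluation ends | Followed to resolution (14.2.4) |
| SAE open at exit | Safety evaluation ends | Monitored until resolved or stable (14.2.5) |
| New SAE within 30 days of last visit | Safety evaluation ends | Must be notified (14.2.5) |
| Later event possibly related to the investigational device | Safety evaluation ends | Reportable at any time (14.2.5) |
| New non-serious event not judged device-related | Safety evaluation ends | Not covered after exit |

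The sections disagree on rows two to five. On the last row they agree, and the event goes unrecorded.

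**2. Whether retreatment falls inside the 30-day window**

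The window runs from the last visit. Section 6.5.2 says only that retreatment is scheduled and gives no time limit, so it may happen inside or outside the window. Outside it, only the device-related route remains. That route depends on the investigator learning of the event and judging it possibly related, and no contact after exit is planned.

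**3. Number of patients**

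Inputs from section 7.2: 90% efficacy in both arms, margin 13 points, one-sided alpha 5%; 80% power from section 7.3.

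The plan's own figure reproduces: n = (1.645 + 0.842)² × 2 × 0.90 × 0.10 / 0.13² = 6.185 × 0.18 / 0.0169 = 65.9, rounded up to 66 per group. Adding 20% gives 66 × 1.2 = 79.2, rounded up to 80.

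Expected failures by 24 months: 80 × (1 − 0.90) = 8 per arm, or 16 of 160.

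This is an upper bound on the expected number whose safety evaluation the sentence cuts short before 24 months:

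- Every emergency exit at V3 or V4 is counted as a 24-month failure, so these exits are a subset of the 8.
- Failures first found at V5 lose none of the 24-month observation.
- The sentence is not in the non-emergency branch, where the coordinator's advice comes before any exit.

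The documents do not give the share of failures handled as emergencies. They also give no efficacy assumption at 3.5 years, so V6 exits cannot be counted.

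**4. Observation time for each early exit**

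Exit at 6 months leaves (24 − 6)/24 = 75% of the 24-month period unobserved; exit at 12 months leaves (24 − 12)/24 = 50%. Some of that time follows retreatment, when the allocated sealer may no longer be in place.

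**The case against.** There is a coherent way to read the text. Section 6.5.2 ends scheduled evaluations for a patient who has left; section 14.2.4 governs AEs already open; section 14.2.5 governs reporting after exit. Its 30-day clause runs from each patient's own last visit, so it reaches early leavers, and its next sentence reaches device-related events without time limit and without a seriousness threshold. On this reading the only real gap is new non-serious events that nobody attributes to the device. The failure episode is not lost either: AEs are recorded and the tooth is examined at the visit before exit, and at V3 and V4 the failure is carried into the primary endpoint.

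Much of this stands. It rules out some stronger inferences that a reader might draw:

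- *Harm found at retreatment goes unreported.* Section 14.2.5 keeps it reportable if judged possibly device-related.
- *Recording stops at the failure visit itself.* It does not.
- *Section 5.1 is breached.* Its wording gives a planned horizon, which any early exit shortens.
- *Every notified failure ends safety evaluation under this sentence.* The sentence is only in the emergency branch at V3, V4 and V6. Other failures withdrawn at 6 or 12 months (section 7.7.11) leave active monitoring only through the general rule in section 14.

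What the objection does not remove is that the protocol never says the coherent reading applies. The 6.5.2 sentence names safety explicitly and has no qualifier or cross-reference, so a site could reasonably follow it as written.

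**Conclusion.** The point holds as an internal conflict in safety collection. In the emergency branch at V3, V4 and V6, one section ends safety evaluation and another continues it. The practical exposure is open AEs no longer followed, post-exit SAEs missed, and new non-serious events not judged device-related that neither section captures.

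The scale is limited and not fully known. The expected number to 24 months is at most about 8 of 80 per arm, assuming the planned 90% efficacy and all 80 patients observed; the true number is lower by an amount the documents do not give.

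A reader might go further and conclude that a worse sealer would look safer. The documents do not support that. If early exits differ by arm, the comparison in section 7.7.6 rests on unequal observation time and could be biased. But nothing shows that failing patients carry more sealer-related harm. Section 4.4 attributes pain from under- or over-filling to causes other than the cement, and retreatment may add procedure-related events of its own. Neither the direction nor the size of any bias is established.

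The primary efficacy analysis is not affected. The change should be made because this is a first-in-human device trial and the correction is cheap.

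**What to change.** Reconcile section 6.5.2 (V3, V4 and V6) and the general provisions of section 14 with sections 14.2.4 and 14.2.5. One way is to limit the 6.5.2 sentence to performance and scheduled evaluations, and to cross-refer to 14.2.4 for open AEs and to 14.2.5 for reporting after exit. The sponsor should also state whether new non-serious events after exit are meant to be collected, so that any gap is deliberate. None of this changes a treatment, retreatment or withdrawal decision.

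In section 7.7.6, report AEs with the observation time available in each arm. This is needed whatever wording is chosen, because a 30-day window does not restore the 18 or 12 months left unobserved after an exit at 6 or 12 months.

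The cost is minor wording and eCRF changes, a check that safety entries can still be made after the end-of-trial form, and some later safety entries for the few patients who exit early.
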